This will be an open-label, single-arm, multicenter, 2-year Phase IV trial. Subjects meeting the eligibility criteria during a pre-baseline screening period of up to -3 months before baseline (Day 1 of treatment) will receive an initial treatment course in Year 1 and a retreatment course in Year 2.

Subjects will attend visits for assessments at end of Months 1,2,3,6, 12 following Baseline (Day 1 of treatment) and at end of Month 15,18, 24 following second treatment course (Month 1 of Year 2), respectively. Subjects will attend visits for blood sample as per mandatory monitoring at pre-Baseline and at Months 2, 6, 12, 14, 18 and 24. The primary endpoint(s) will be assessed during the first 6 months, secondary and tertiary endpoints will be assessed up to Month 24.

CCI [REDACTED]

Visit schedules for efficacy and safety assessments are detailed in the Schedule of Assessments.

Planned number of subjects: Approximately 265 subjects are planned to be included

Primary endpoint(s):

- Differences in the counts of combined unique active (CUA) MRI lesions during the first 6 months (i.e. during periods months 1-6, 2-6, 3-6) compared to baseline (i.e. the period screening to baseline)

Secondary endpoints:

- Characterization of immune cell subsets count at the end of 3, 6, 12, 15, 18 and 24 months compared to baseline

Tertiary endpoints:

Safety:

- Occurrences of treatment-emergent adverse events (TEAEs) and serious adverse events (SAEs) including and up to 24 months

Clinical:

- Changes in Symbol Digit Modality Test (SDMT) outcome at the end of 6, 12, 18 and 24 months compared to baseline
- Disability evolution as measured by Expanded Disability Status Scale (EDSS)/ Kurtzke Functional System (KFS), 9-Hole Peg Test (9HPT), Timed 25-Foot Walk (T25FW) at the end of 6, 12, 18 and 24 months compared to baseline
- Annualized Relapse Rate (ARR) between baseline and 24 months
- Changes in CUA lesions during the following post-baseline periods –compared to baseline period (i.e. the period from screening to baseline):
 - Period of month 6 to month 12
 - Period of month 1 to month 12
 - Period of month 18 to month 24
 - Period of month 1 to month 24Further periods and comparisons may be defined in the SAP
- Number of CUA lesions during the baseline and post-baseline periods as defined above
- Changes in active T1 gadolinium (Gd)+ lesion count at the end of 1, 2, 3, 6, 12, 15, 18 and 24 months compared to baseline

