5.2 Discussion of Trial Design

This will be an open-label, single-arm, multicenter, 2-year Phase IV trial. This trial will include a pre-Baseline screening period up to -3 months prior to drug administration, followed by an initial treatment course in Year 1 and a retreatment course in Year 2. Baseline is defined as the day on which the first dose of Mavenclad[®] is administered. Subjects will attend visits for assessments at the end of Months 1, 2, 3, 6, and 12 following Baseline and at the end of Month 15, 18, 24 following second treatment course (Month 1 of Year 2), respectively. Subjects will attend visits for blood sample as per mandatory monitoring at pre-Baseline and at Months 2, 6, 12, 14, 18 and 24.

Re-screening will be allowed once for those subjects who do not meet the inclusion/exclusion criteria within the above specified time limits. The Medical Monitor must promptly inform the Sponsor about requests and reasons for re-screening.

Subjects with RMS will receive Mavenclad[®] 3.5 mg/kg body weight over 2 years, administered as 1 treatment course of 1.75 mg/kg per year. Each treatment course will consist of 2 treatment weeks, one at the beginning of the first month and one at the beginning of the second month of the respective year. Each treatment week consists of 4 or 5 days on which a subject receives 10 mg or 20 mg (one or 2 tablets) as a single daily dose, depending on body weight as noted in SmPC (see [Appendix 13: Mavenclad Posology](#)).

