8.5 Description of Statistical Analyses

8.5.1 General Considerations

All analyses of all endpoints except the primary analysis, will be performed exploratively and, differences with a p-value of 0.05 or less will be considered nominally statistically significant.

Parameter estimates with associated 95% confidence intervals (CIs) will be reported in each analysis. No correction for multiple testing will be applied for any secondary or tertiary analysis.

Subjects' demographic factors and baseline clinical characteristics will be summarized with the following measures: mean with standard deviation, minimum and maximum for normally distributed continuous variables, median with interquartile range, minimum and maximum for other continuous variables and counts with percentages for categorical variables.

As the secondary and tertiary analysis set concerns repeated measurements of outcomes for each individual, it is likely that observations pertaining to each individual will be correlated. Furthermore, as this is a multi-center trial, it is likely that clustering of individuals within trial sites will produce an additional source of correlation. Mixed-effects regression, whereby a three-level hierarchical model is specified for observations within subjects within trial sites, will be used to account for within-subject and within-center correlation (Gibbons, 2010).

The parametric assumptions underlining the regression models specified will be examined. Should these assumptions be violated, alternative methods, such as non-parametric approaches, may be considered in addition.

Assessment Schedules

It is likely that the second year treatment may be delayed substantially due to grade 3 or 4 lymphopenia for a small number of subjects for whom the second dose is not required immediately. Due to the need for a finite follow-up period, a buffer of 3 months is given for subjects who do not receive the second treatment at the specified time. Subjects for whom treatment is delayed by over 3 months may not have all assessment data captured and as such, these observations will be treated as missing in efficacy analyses.

In each analysis, should assessment be delayed, subjects' assessment data will be treated as though it occurred at the time point specified and inferences will be conducted accordingly.

Missing Data

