14.3.2 CUA lesion count

CUA lesion counts for the Sequential Visit Periods are defined in the Section 9 "Definition of Study Periods" and "Data Handling of MRI data".

Analysis (Analysis Set)	Derivation	Statistical Analysis Methods	Missing data handling
Tertiary endpoint: Annualized CUA lesion count by Visit			
Tertiary (FAS)	Absolute CUA lesion count at Month i Visit, where i= 0, 1, 2, 3, 6, 12, 15, 18 and 24.	Mixed-effects linear model for repeated measures for the absolute values over 24 months with the following adjusting factors: 
 • Baseline score, • Age (in years), • EDSS at Baseline (≤ 3, > 3), • Visit[§], • Time between scans (years), • Pooled center, • Within-subject correlation. Estimated Least Square Means (LS Means) and corresponding Standard Errors (SE) will be presented by Visit including 95% CI.	Same as for mixed effect linear model with repeated measures in Section 14.3.1
Tertiary (FAS by subgroup "High-relapse activity")			
Tertiary (FAS by subgroup "Previous treatment with DMDs")			
§=Sequential Visit Periods			

Mixed-effects linear model for repeated measures

As defined in Section 14.3.1 applying adaptations to the endpoints, factors and covariates listed in the table above.

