The increase will be defined as sustained when it occurs on two post-Baseline Visits, which are at least 166 days (6 months × 30 - 14 days Visit Window) apart and no observations at any other Visit (including unscheduled Visits) in between are less than the defined increase.

The occurrence of a 6MCDP is defined as:

- Yes: sustained increase in EDSS score that started during the Treatment Period,
- No: at least 2 post-Baseline EDSS assessments that are 166 (or more) days apart are available and no sustained EDSS progression that started during the Treatment Period,
- Unknown: Otherwise.

Start date of the 6MCDP is the start date of the first sustained increase in EDSS.

MRI activity:

- Yes: At least one T1 Gd+ at any scan assigned to Month 6, Month 12, Month 18, Month 24 Visit, or at least one active T2 during any of the following Periods: Baseline to Month 6, Month 6 - Month 12, Month 12 - Month 18, Month 18 – Month 24 Visits.
- No: T1 Gd+ = 0 at all scans assigned to Month 6, Month 12, Month 18, Month 24 Visit that have a value and at least one T1 Gd+ value from Month 18 or Month 24 Visit available, and all active T2 = 0 during any of the following Periods: Baseline - Month 6, Month 6 - Month 12, Month 12 - Month 18, Month 18 - Month 24 Visits that have a value and at least one active T2 value from periods Month 12 - Month 18 or Month 18 - Month 24 Visits available.
- Unknown: Otherwise.

CCI [REDACTED]

[REDACTED]

[REDACTED]

[REDACTED]

CCI [REDACTED]

CCI [REDACTED]

Brain Atrophy

- Yes: Annualized percentage brain volume change during the Treatment Period < -0.4% (see Section 14.3.11),
- No: Annualized percentage brain volume change during the Treatment Period ≥ -0.4%,
- Unknown: Otherwise.

Analysis of NEDA

NEDA and its components will be analyzed with a logistic regression with adjusting factors age (in years) and EDSS at Baseline (≤3, >3).

Analysis (Analysis Set)	Derivation	Statistical Analysis Methods	Missing data handling
Tertiary endpoint: NEDA at 24 months			
Tertiary (FAS)	NEDA-3 during Treatment Period	Logistic regression: Adjusting factors: 
 • Age (in years), • EDSS at Baseline (≤3, >3). Estimated probability and corresponding Standard Errors (SE) will be presented including 2-sided p-values and 95% CIs.	Unknown status: Subjects with an unknown status will be excluded from the logistic regression. Missing covariate or stratification information will be imputed as specified in Section 9.

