Tertiary (FAS)	NEPAD during the Treatment Period	Same as in the Tertiary Analysis of NEDA (Section 14.3.12)	Same as in the Tertiary Analysis of NEDA (Section 14.3.12)
Tertiary (FAS)	Confirmed T25FW progression during the Treatment Period		
Tertiary (FAS)	Confirmed 9HPT progression during the Treatment Period		

14.3.14 Changes in SDMT outcome at the end of 6, 12, 18 and 24 months compared to Baseline

The SDMT (Symbol Digit Modalities Test) presents a series of nine symbols, each paired with a single digit in a key at the top of a standard sheet of paper. An adapted version of the test is presented in the protocol. Subjects are asked to voice the digit associated with each symbol as rapidly as possible for 90 sec. The SDMT score is the number of correct digits over the 90 sec time span.

Minimal decline in cognitive function is defined by:

- Yes: Change from Baseline in SDMT ≥ -4 at the Month 24 Visit
- No: Change from Baseline in SDMT < -4 at the Month 24 Visit
- Missing: Baseline or Month 24 Visit value is not available

The observed results and changes from Baseline in the SDMT and scaled scores of the SDMT will be tabulated by Visit for the FAS (see Section 18.2).

Analysis (Analysis Set)	Derivation	Statistical Analysis Methods	Missing data handling
Tertiary endpoint: Changes in SDMT outcome at the end of 6, 12, 18 and 24 months compared to Baseline			
Tertiary (FAS)	Change from Baseline in SDMT (raw and scaled scores) at Month i Visit, where i= 6, 12, 18 and 24.	Descriptive summary statistics.	
	Minimal Decline in Cognitive Function at Month 24 Visit compared to Baseline	Descriptive summary statistics	Missing values will be included in the denominator and presented as a separate category.

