14.3.18 Annualized Relapse Rate (ARR) between Baseline and 12/24 months

The unadjusted ARR will be calculated for the Treatment Period, Course 1 Treatment Period and Course 2 Treatment Period.

The unadjusted ARR for a subject i is defined as the number of relapses per year:

- ARR for subject i = number of relapses during the Period / person-years of subject i ,
- Person-years for subject i = Period (in days) / 365.25.

The unadjusted population ARR is the mean of all subject's ARR. The unadjusted ARR will be calculated for all relapses, as well as the qualifying relapses (ARR_{qual}), as reported in the eCRF.

Relapses will be counted for the defined time Period, if the date of onset of the relapse is within the defined time Period. Incomplete or missing onset dates will be imputed as specified in Section 9.

The number of subjects with (qualifying) relapses, the number of (qualifying) relapses, person-years and the unadjusted population ARR will be presented for the Treatment Period, Course 1 Treatment Period and Course 2 Treatment Period. Also, the number of subjects with relapses and number of relapses which were treated with steroids or leading to hospitalization will be presented separately. For the Interim Analysis the different relapse counts up to the month 6 Visit will be presented without the ARR.

In addition, the relapse rate will be analyzed using a Poisson regression model with count of relapses as dependent variable and with fixed effects for age (in years) and EDSS at Baseline (≤ 3 , > 3). The log of the duration of the treatment Period (precision in days) will be the offset variable in the model.

Analysis (Analysis Set)	Derivation	Statistical Analysis Methods	Missing data handling
Tertiary endpoint: Annualized relapsed rate (ARR) between Baseline and Month 12 and Month 24			
Tertiary (FAS)	ARR during the Treatment Period	Poisson regression for number of relapses. Adjusting factors: 
 • Age (in years), • EDSS at Baseline ($\leq 3 / > 3$). • Log of the duration of the Treatment Period (in days) as offset. Estimated mean ARR and corresponding Standard Errors (SE) will be presented, including 2-sided p-values and 95% CIs. In addition, the unadjusted ARR will be presented descriptively.	The analysis will consider the different observation Periods of early withdrawals by including the treatment Period as offset in the analysis. This strategy is assuming MAR.

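### The planned p-values on the estimated ARR and on the NEDA and NEPAD probabilities have no stated null in a single-arm trial and cannot support a drug effect

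*SAP*

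**What the plan says.** Protocol 5.2 describes the design: "This will be an open-label, single-arm, multicenter, 2-year Phase IV trial". There is no control group.

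- **ARR.** SAP 14.3.18 fits a Poisson regression of the relapse count on age and EDSS category, with this offset: "Log of the duration of the Treatment Period (in days) as offset". The output is: "Estimated mean ARR and corresponding Standard Errors (SE) will be presented, including 2-sided p-values and 95% CIs". It applies to 8 rows.
- **NEDA.** SAP 14.3.12 fits a logistic regression on age and EDSS category. The output is: "Estimated probability and corresponding Standard Errors (SE) will be presented including 2-sided p-values and 95% CIs". It applies to 9 rows: four versions of NEDA and five components.
- **NEPAD.** SAP 14.3.13 refers back to the NEDA analysis for 3 rows: NEPAD itself and the confirmed T25FW and 9HPT progressions.

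For every endpoint except the primary one, Protocol 8.5.1 says that "differences with a p-value of 0.05 or less will be considered nominally statistically significant".

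SAP 14.3.2 treats an absolute level differently. For the CUA lesion count by visit the output is: "Estimated Least Square Means (LS Means) and corresponding Standard Errors (SE) will be presented by Visit including 95% CI". There is no p-value.

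**The concern.** A p-value needs a null hypothesis. The lesion-change analyses have one: they compare post-baseline periods with the Baseline Period, so no change, or a ratio of 1, is a meaningful reference. An ARR over the treatment period, or the proportion with NEDA at 24 months, has no such anchor. The models contain no treatment term, no pre/post term and no historical value.

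The risk is in how the results are read. SAP 14.1.1 adds two-sided p-values to the primary analysis so that it can be compared with the secondary and tertiary ones. Tertiary p-values are therefore expected to be read beside the primary result. SAP Section 4 allows for use of the planned analyses in submissions and manuscripts. ARR and NEDA are familiar clinical outcomes, and a very small p-value beside either could be taken as evidence of efficacy.

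**Working it through.** The visible documents give no null value, expected ARR or expected NEDA rate for these analyses, so there is no planned figure to reproduce. The check asks what each p-value would test under each reasonable reading.

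**Inputs.** Sample size from the Protocol synopsis: "Approximately 265 subjects are planned to be included". The log-days offset and the factor of 365.25 days per year come from SAP 14.3.18. Assumed: full two-year follow-up, so 265 × 2 = 530 person-years; no covariate effect in the closed forms; ARR from 0.1 to 3.0; NEDA rates from 20% to 80%; and 200 to 265 subjects in the logistic models, because 14.3.12 excludes subjects with unknown status.

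**Reading 1: ARR, zero on the log scale.** z = ln(ARR / null) × √(ARR × 530). With the offset in log days the null is 1 relapse per day, or 365.25 per year. Rescaled to years, the null is 1 per year.

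| True ARR | Expected events | z against 1 per day | z against 1 per year |
|---|---|---|---|
| 0.1 | 53 | -59.7 | -16.76 |
| 0.2 | 106 | -77.3 | -16.57 |
| 0.9 | 477 | -131.2 | -2.30 (p = 0.021) |
| 0.95 | 504 | -133.6 | -1.15 (p = 0.25) |
| 1.0 | 530 | -135.8 | 0.00 (p = 1) |
| 1.1 | 583 | -140.2 | +2.30 (p = 0.021) |
| 2.0 | 1060 | -169.5 | +22.57 |
| 3.0 | 1590 | -191.5 | +43.81 |

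For example, at ARR 0.2: ln(0.2 / 365.25) = -7.51, √106 = 10.30, and the product is -77.3. Even an ARR of 0.002, about one expected event, gives z = -12.5 against 1 per day.

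A Poisson GLM fitted to one simulated dataset (265 subjects, 720 days each, centred age and EDSS, true ARR 0.95) confirms the dependence on the time unit. The estimate and interval are the same with either offset: 0.933 (95% CI 0.853 to 1.019). The test is z = -131.4 with days, and z = -1.54 (p = 0.125) with years.

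**Reading 2: NEDA and NEPAD, zero on the logit scale.** The null is 50%, and z = ln(p / (1 - p)) × √(n p (1 - p)).

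| Rate | n = 265 | n = 200 |
|---|---|---|
| 30% or 70% | z = ∓6.32, p = 2.6e-10 | z = ∓5.49, p = 4.0e-8 |
| 43% or 57% | z = ∓2.27, p = 0.023 | z = ∓1.97, p = 0.048 |
| 44% or 56% | z = ∓1.95, p = 0.051 | z = ∓1.69, p = 0.090 |
| 50% | p = 1 | p = 1 |

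The p-value falls below 0.05 outside about 44% to 56% at n = 265, and outside about 43% to 57% at n = 200. A 30% rate and a 70% rate give the same p-value.

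**Reading 3: the p-values belong to the age and EDSS coefficients.** They then test whether relapse rate or NEDA varies with age or EDSS. That is a legitimate question, but it does not concern the drug.

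**Count.** 8 + 9 + 3 = 20 visible rows. On no reading does any of them test a drug effect.

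**The case against.** Several counter-arguments have weight.

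- **The reference values are inferred.** Neither 1 relapse per day nor 50% is written in the SAP. Both follow from the usual software default. The negative binomial models in SAP 14.1.2 and 14.3.1 mention p-values together with the estimated fixed effects, so the shorter wording here may mean the age and EDSS terms. This stands, and is why the third reading is kept. It could also point the other way, because 14.3.12 and 14.3.18 lack that fixed-effects wording.
- **The extreme z-values depend on one route.** 14.3.18 defines person-years as days divided by 365.25 and calls the output an ARR. The test might be done on the annual scale, where an ARR of 0.95 gives p = 0.25. This also stands, but 1 per year is no better justified as a reference.
- **Protocol 8.5.1 speaks of differences.** A level is not a difference. Nothing visible says that an ARR or a NEDA rate will be declared significant, or that these p-values will be used as evidence of effect.
- **The consequences are small.** The endpoints are tertiary and exploratory, and estimates, SEs and confidence intervals are already planned for every row.
- **Some text is redacted.** Part of the significance-level paragraph in SAP Section 9 is blacked out, so the absence of a null can be asserted only for the visible text.

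None of these supplies a null that would make the p-values informative about the drug.

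**Conclusion.** The point holds for all 20 visible p-values: they attach to absolute levels, or to unlabelled covariates, and cannot support a drug effect. The 44% to 56% band assumes 265 evaluable subjects, no covariate effects and a Wald test on the logit scale. The ARR figures assume 530 person-years and a Wald test on the log scale.

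A reader might go further and infer that nominal significance on all these rows is unrelated to whether the drug works, or that the plan will declare every ARR row significant. The documents do not support that. Only ARR tested against 1 per day is rejected at every realistic rate. The NEDA and NEPAD p-values, and ARR against 1 per year, move with the observed level, which the drug may influence. Their fault is an arbitrary reference that treats a low rate and a high rate alike. Protocol 8.5.1 does not explicitly apply its significance label to levels.

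Estimates and confidence intervals are unaffected, and the primary analysis is not touched. The matter is worth correcting because the output would be uninterpretable as specified, but it does not threaten the trial's main conclusion.

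**What to change.** In SAP 14.3.12, 14.3.13 and 14.3.18:

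1. Delete the two-sided p-values on the estimated ARR and on the estimated probabilities. Report the estimate, SE and 95% CI, as 14.3.2 does. Alternatively, pre-specify a reference value for each endpoint and justify it.
2. If p-values for age or EDSS are wanted, keep them in a separate part of the table, labelled as covariate effects.
3. As a clarification only, state how the Poisson estimate is turned into an annual rate, for example with log(days / 365.25) as the offset. This changes no estimate or interval.

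The cost is SAP wording and table shells. No data collection or model changes. The tertiary tables lose up to 20 p-values.

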15.1 Adverse Events

Treatment emergent adverse events (TEAEs) are those events with onset dates occurring within the Treatment Period (see Section 9 for definition).

All analyses described in Section 15.1 will be based on TEAEs if not otherwise specified.

Incomplete AE-related dates will be handled as follows:

- In case the onset date is missing completely or missing partially and the onset month and year or the onset year are equal to the start of study medication, then the onset date will be replaced by the start date of study medication or AE resolution date whichever is earlier.
- In all other cases the missing onset day or missing onset month will be replaced by 1.
- Incomplete stop dates will be replaced by the last day of the month (if day is missing only), if not resulting in a date later than the date of subject's death. In the latter case the date of death will be used to impute the incomplete stop date.
- In all other cases the incomplete stop date will not be imputed.

15.1.1 All Adverse Events

TEAEs will be summarized using MedDRA PT as event category and MedDRA primary SOC body term as Body System category overall and by HRA subgroups (HRA and non-HRA).

Unless otherwise stated, adverse events will be displayed in terms of frequency tables: PT and primary SOC in alphabetical order.

Adverse events related to study treatment are those events with relationship missing, unknown or related.

The following overall frequencies of subjects with the corresponding TEAEs will be prepared. In addition, the tables will be provided by PT and primary SOC in alphabetical order:

- Any AE,
- Any study treatment related AEs,
- Any serious AEs,
- Any non-serious AEs,
- Any study treatment related serious AEs,
- Any AE by severity (mild, moderate, severe),
- Any study treatment related AE by severity (mild, moderate, severe),
- Any AEs leading to death (AEs with outcome “fatal”),
- Any study treatment related AEs leading to death (AEs with outcome “fatal”).

Summary table for non-serious adverse events applying frequency threshold of 5% will be provided by SOC and PT.

Summary tables for serious and non-serious adverse events applying frequency threshold of 5% sorted by decreasing frequency will be provided by PT.

All AE by worst severity (Mild or worse, moderate or worse, severe) will be presented by SOC and PT.

All AEs including non-treatment emergent AEs will be listed by subject for the SAF.

Exposure Adjusted Incidence Rate

Exposure adjusted incidence rates (EAIR) are calculated as number of subjects with AE divided by the sum of the individual times in years of all subjects in the safety population from start of study medication to first onset of AE or end of treatment Period, whichever occurs first.

The exact Poisson 95% confidence intervals for the EAIR are calculated using the relationship between the Poisson and the Chi-square distribution (Ulm [1], 1990):

$$LCI = \frac{\chi_{2n, \frac{\alpha}{2}}^2}{2 \times t'}$$
$$UCI = \frac{\chi_{2(n+1), 1 - \frac{\alpha}{2}}^2}{2 \times t'}$$

where t is the sum of the individual times in years of all subjects and n is the number of subjects with a specific AE for the EAIR, which will be the basis for the number of the degrees of freedom for the chi-square quantile for the upper tail probability χ^2 .

Exposure adjusted incidence rates of TEAEs will be presented overall and by SOC and PT.

The following table will be provided:

- Exposure adjusted incidence rates of AEs by SOC and PT.

